5.4 Blinding

This is an open-label study; therefore, blinding is not applicable.

5.5 Stopping Rules

5.5.1 Anaphylactic Reaction

If an anaphylactic reaction occurs in any subject, study drug will be discontinued for that subject. The subject will follow the schedule of assessments for the Early Discontinuation Visit and the 1-Week and 1-Month Post-treatment Follow-up Visits (see Schedule 3). Other enrolled subjects will continue with study drug administration and procedures.

5.5.2 Thrombotic or Thromboembolic Event

If a thrombotic or thromboembolic (T/TE) event occurs in any subject, no further enrollment will occur pending a complete review of all available data. Other enrolled subjects will continue with study drug administration and procedures. Following a safety review of the T/TE event, study enrollment may be restarted if it is determined that the event is not related to study drug or other C1 inhibitors, which may have been administered for an angioedema attack.

If a T/TE event occurs in any subject, study drug administration for that subject will be interrupted; however, other study procedures will continue, as deemed appropriate by the Investigator in conjunction with the Sponsor. Investigators will comply with protocol-defined algorithms to assist in the diagnosis and management of all suspected T/TE events (see Appendix 2). Following a complete medical review by the Sponsor in conjunction with the Investigator, dosing with study drug may be resumed to complete a total of 24 doses if it is determined that the T/TE event is not related to study drug. Study procedures, including PK/PD testing, will resume relative to dosing. If study drug cannot be restarted within 30 days of temporary interruption, the subject will be discontinued from treatment and will follow the schedule of assessments for the Early Discontinuation Visit and the 1-Week and 1-Month Post-treatment Follow-up Visits (see Schedule 3).

Protocol 0624-209 with Amendments 1, 2, 3, 4, and 5 CINRYZE (C1 inhibitor [human])

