| Immunogenicity (C1 INH antibody) | X | | X |
| Quality of life questionnaire (AE-QoL) | X | | |
| PK/PD assessments | X ^f | | |

AE-QoL=angioedema quality of life; aPTT=activated partial thromboplastin time; BP=blood pressure; C1 INH=C1 inhibitor; INR=international normalized ratio; PD=pharmacodynamics; PK=pharmacokinetics; PT=prothrombin time; SAE=serious adverse event

- a: If a subject prematurely discontinues investigational product, regardless of the reason, the Early Discontinuation Visit procedures listed in Schedule 3 are to be performed as completely as possible. Whenever possible, all discontinued subjects should also complete the 1-Week and 1-Month Post-treatment Follow-up visits.
- b: Vital signs will be measured using standard methods at each study site.
- c: All females of childbearing potential (in accordance with standards at the site).
- d: Subjects who prematurely discontinue should complete the study diary on the day of discontinuation.
- e: Adverse events will be collected through 7 days after the last dose of investigational product. Investigators will report all serious adverse events (SAEs) that occur up to 30 days after the last dose of study drug to PAREXEL International Pharmacovigilance. In addition, SAEs considered by the Investigator to be related to study drug that occur >30 days after the last dose will be reported.
- f: If a subject prematurely discontinues on a blood sample collection day for PK/PD assessments (see Schedule 4), every effort should be made to collect the PK/PD sample(s) according to schedule. If a subject discontinues on a day when PK/PD assessments are not scheduled, a single PK/PD blood sample should be collected with sampling time recorded in the CRF.

Schedule 4: Blood Sample Collection Time Points for PK/PD Assessments

| C1 INH Antigen (Protein Volume), Functional C1 INH Activity (Potency), | T | REATMENT PERIO | D (BY STUDY WEE | K) | Early |
|---|----------------|----------------|-----------------|-----------------|--------------------------|
| and Complement C4 | Week 1 | Week 2 | Week 3 | Week 12 | Discontinuation Visit |
| Sample Time | Dosing Visit 1 | Dosing Visit 3 | Dosing Visit 5 | Dosing Visit 24 | [If Applicable] |
| Prior to infusion of study drug | X ^a | X | X | X | |
| 0.5 hour after start of infusion | X ^b | | | X ^b | |
| 1 hour after start of infusion | X ^c | | | X ^c | |
| 2 hours after start of infusion | X ^c | | | X ^c | X g |

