Throughout the trial, a study diary will be used by subjects (or caregivers) to record specific information about any angioedema attack symptoms and details on the self-administration of investigational product (see Section 6.11). Because of the potential to precipitate an angioedema attack, subjects will be requested to postpone elective medical procedures (eg, dental work) and avoid other known attack triggers while participating in the study (see Section 6.10).

Safety will be assessed by monitoring adverse events and changes in physical examinations, vital signs, and clinical safety laboratory testing. In addition, subjects will be monitored for the development of antibodies to C1 INH. If clinically indicated, study personnel may perform examinations to actively monitor subjects for possible venous thromboembolism or other thrombotic or thromboembolic (T/TE) events. Stopping rules are provided in Section 5.5.

Protocol 0624-209 with Amendments 1, 2, 3, 4, and CINRYZE (C1 inhibitor [human])

In this study, angioedema attacks will not be reported as adverse events unless the attack meets the definition of a serious adverse event (see Section 9.1.4).

Adverse events will be recorded from the time the informed consent is signed through 7 days after the last dose of investigational product. This includes events occurring during the screening phase of the study, regardless of whether or not the investigational product is administered. In addition, the investigator will report all SAEs that occur through 30 days after the last dose of investigational product to PAREXEL International Pharmacovigilance and the respective Independent Reviewing Authority according to local reporting requirements.

Post-treatment follow-up visits will be performed 1 week (± 1 day) and 1 month (30 ± 2 days) after the last dose of study drug. If a subject prematurely discontinues investigational product, regardless of the reason, the Early Discontinuation Visit procedures listed in Schedule 3 are to be performed as completely as possible. Whenever possible, all discontinued subjects should also complete the 1-Week and 1-Month Post-treatment Follow-up visits.

The schedules of study procedures are provided as follows:

- Schedule 1: Clinical Study Assessments Screening and Treatment Period;
- Schedule 2: Investigational Product and Self-administration Training;

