6.2 Adverse Event Collection

At each study visit, subjects will be questioned in a general way to ascertain if AEs have occurred since the previous visit (eg, "Have you had any health problems since your last visit?"). Adverse events will be collected from the time informed consent is signed through 7 days after the last dose of investigational product. This includes events occurring during the screening phase of the study, regardless of whether or not the investigational product is administered. In addition, the investigator will report all SAEs that occur through 30 days after the last dose of investigational product to PAREXEL International Pharmacovigilance and the respective Independent Reviewing Authority according to local reporting requirements.

Please refer to Section 9, Adverse and Serious Adverse Events Assessment.

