7.4 Safety Analyses

The following will be assessed:

- Adverse events (including treatment-emergent adverse events).
- Summary statistics and changes from baseline to post-baseline for laboratory testing, vital signs, and, if applicable, any ECG findings will be presented.
- Results of C1 INH antibody testing will be reported for individual subjects and summarized as appropriate.

NOTE: Treatment-emergent events include all adverse events that start during the treatment period (and up to 7 days after the last dose of investigational product) and were not seen at baseline, or were seen at baseline but worsened in frequency and/or severity during the treatment period (and up to 7 days after the last dose of investigational product).

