9.2.4 Serious Adverse Event Collection Time Frame

All SAEs (regardless of relationship to study) are collected from the time the subject signs the informed consent up to 30 days after the last dose of study drug, and must be reported to PAREXEL International Pharmacovigilance within 24 hours of the first awareness of the event.

In addition, any SAE(s) considered "related" to the investigational product and discovered by the Investigator at any interval after the study has completed must be reported to PAREXEL International Pharmacovigilance within 24 hours of the first awareness of the event.

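### After a thrombotic event, a subject discontinued following a long interruption is sent to follow-up visits and AE/SAE windows counted from a last dose given before the interruption, so some have already closed

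*Protocol*

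**What the plan says.** Protocol Section 5.5.2 interrupts study drug for a subject with a T/TE event. Other study procedures go on to the extent that the Investigator and Sponsor think appropriate. Dosing may resume if the event is judged unrelated to study drug. Otherwise a time limit applies: "If study drug cannot be restarted within 30 days of temporary interruption, the subject will be discontinued from treatment". That subject is then directed to the Early Discontinuation Visit and the 1-Week and 1-Month Post-treatment Follow-up Visits of Schedule 3.

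Every clock for that sequence starts at the last dose:

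- Visits (Section 3 and the synopsis): "Post-treatment follow-up visits will be performed 1 week (± 1 day) and 1 month (30 ± 2 days) after the last dose of study drug".
- AEs (Section 6.2): "Adverse events will be collected from the time informed consent is signed through 7 days after the last dose of investigational product". Schedule 3, footnote e, repeats the limit: "Adverse events will be collected through 7 days after the last dose of investigational product".
- Treatment-emergent AEs (Section 7.4): the definition also stops 7 days after the last dose.
- SAEs regardless of relationship (Section 9.2.4): collected "up to 30 days after the last dose of study drug".
- Related SAEs (Schedule 3, footnote e): "SAEs considered by the Investigator to be related to study drug that occur >30 days after the last dose will be reported".

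The visible text gives no other reference date for a subject discontinued after an interruption.

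**The concern.** The last dose comes before the interruption, and the decision to discontinue can come weeks later. The plan can therefore send a subject to a visit whose window has passed and examine that subject after AE collection has formally ended. Schedule 3 shows the conflict within one table: it marks AEs/SAEs for collection at the Early Discontinuation Visit, while footnote e to that row ends AE collection at day 7.

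Collection also comes to depend on a later dosing decision. Take a new non-serious AE on day 15 after the last dose given. If dosing later resumes, the last dose moves forward and the event is collectable. If dosing does not resume, the same event falls outside the window. The site cannot know which applies when the event occurs, and sites may handle it differently.

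The delay is specific to T/TE events. Under Section 5.5.1 an anaphylactic reaction leads straight to discontinuation, so the same visit sequence can be followed. Safety and tolerability is the first-listed objective, T/TE has its own stopping rule, and Section 1.1.2 reports five serious thrombotic events in the overseas open-label prevention study. With a minimum of six completers, one such subject matters to the safety description.

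**Working it through.** This is calendar arithmetic; the plan states no figure to reproduce. Day 0 is the last dose actually given.

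Inputs:

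- Maximum interruption: 30 days (Section 5.5.2).
- 1-Week visit: 7 ± 1, so days 6-8 (Section 3).
- 1-Month visit: 30 ± 2, so days 28-32 (Section 3).
- AE window closes on day 7 (Section 6.2; Schedule 3, footnote e).
- SAE window closes on day 30 (Section 9.2.4).
- Lag L from last dose to start of interruption: 0-4 days. This is an assumption, taken from dosing every 3 or 4 days.

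Step 1, earliest conflict. The AE window is shut for any decision from day 7 + 1 = 8. The 1-Week window is shut for any decision from day 8 + 1 = 9. Counted from the start of the interruption, the AE window stays open for 7 − L days (7 down to 3) and the 1-Week window for 8 − L days (8 down to 4). The conflict therefore does not need the full 30 days.

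Step 2, discontinuation at the maximum. Decision day D = L + 30. Time since closing is D − 8 for the 1-Week visit, D − 7 for AEs and D − 30 for SAEs. Time left for the 1-Month visit is 32 − D.

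| L | D | 1-Week closed for | AE closed for | SAE closed for | 1-Month window |
|---|---|---|---|---|---|
| 0 | 30 | 22 days | 23 days | 0 (ends that day) | 2 days left |
| 1 | 31 | 23 days | 24 days | 1 day | 1 day left |
| 2 | 32 | 24 days | 25 days | 2 days | last day |
| 3 | 33 | 25 days | 26 days | 3 days | closed 1 day |
| 4 | 34 | 26 days | 27 days | 4 days | closed 2 days |

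Step 3, where data would be lost. The date algorithm for treatment emergence in SAP Appendix III has no upper cut-off. It would not remove a late event that had been recorded. The exposure is therefore at collection.

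**The case against.** Much of the case on the other side stands.

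- A reader might infer that the T/TE event itself goes unfollowed. The documents do not support that. On the 0-4 day assumption it falls inside the AE window. Section 9.1 has all AEs followed to closure even after the subject leaves the study, Section 6.15.1 follows subjects who stop because of an AE until it is resolved or stable, and related SAEs are reportable with no end date.
- A reader might infer that later AEs cannot be collected at all. That is too strong. Other procedures may continue, subjects are asked about AEs at each study visit, and a site that still expects to restart has no reason to stop recording. But continued procedures are discretionary, Section 5.5.2 ties their resumption to dosing, and none of this extends a window.
- A reader might infer that the 1-Month visit always falls on or before the Early Discontinuation Visit. It does not: with a lag of 0 or 1 day, 2 days or 1 day remain.
- Thirty days is a maximum. Section 6.15 allows withdrawal at any time, and a decision by day 7 avoids the conflict.
- Section 3, Section 6.15 and Schedule 3 footnote a ask discontinued subjects for the two follow-up visits only where possible. The 1-Week visit's three items (medications, attack diary, AEs) are also on the Early Discontinuation Visit list, so missing it loses no unique type of assessment.
- Measured from exposure, these subjects face the same cut-offs as everyone else; nobody's window is shortened.
- Appendix 2, on managing suspected T/TE events, survives only as a heading in the text available, so it may contain relevant instructions.

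These points limit the consequence. They do not supply a reference date, and they do not settle whether an event during an unresolved interruption should be recorded.

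**Conclusion.** The conflict is real but limited in reach. Section 5.5.2 directs a subject to a visit sequence that, on the protocol's own figures, cannot be completed within its windows once the decision comes on day 9 or later. AE collection has formally closed from day 8. At the 30-day maximum the AE window has been shut for 23-27 days and the 1-Week window for 22-26 days, while the SAE and 1-Month windows are at or near their end.

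Exposed are new non-serious AEs after day 7 and new SAEs after day 30 that are not judged related, in a subject who has had the risk for which the protocol has a separate stopping rule. Whether they are collected depends on a later dosing decision and on discretionary procedures.

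The maximum-case figures rest on the assumed 0-4 day lag; the day-8 and day-9 thresholds do not. The conclusion also assumes that Appendix 2 gives no separate reference date. A reader might infer that all four windows must restart from the date of the decision. The documents do not support that as the only repair: it would set a new rule and would carry the AE window beyond the 7-day limit in Section 7.4.

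**What to change.** Reconcile Section 5.5.2 with Sections 3, 6.2, 7.4 and 9.2.4 and with Schedule 3 (including footnote e) on the reference date for these visits and windows after an interruption.

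State that AEs and SAEs are recorded throughout the interruption, up to and including the Early Discontinuation Visit, whether or not dosing restarts. This removes the dependence on a later decision and the conflict between the Schedule 3 row and its footnote.

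Add days since last dose to the SAP's AE listing (Listing 16.2.7.1), so that late events can be told apart from those within the 7-day treatment-emergent window of Section 7.4.

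The permitted length of interruption and the decision to restart are left as they are. The cost is protocol wording, one listing column, and a few more weeks of AE recording for a rare subject.

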6 STUDY PROCEDURES

Subjects meeting the eligibility criteria listed in Section 4 may be enrolled in the study after the nature and purpose of the protocol have been explained and written informed consent to participate has been voluntarily granted by the subject or permission for minors has been granted by a parent/legal guardian and assent has been provided by appropriate subjects (Section 14). For subjects who are screened (ie, those with signed written informed consent) but not enrolled, demographic information and reason for screen failure will be recorded in the CRF. Schedule 1, Schedule 2, and Schedule 3 provide details of study procedures and clinical assessments, and Schedule 4 provides timing of PK/PD blood sampling.

NOTE: It is possible for the Screening Visit and Dosing Visit 1 to occur on the same day. If this occurs—to prevent repetition of protocol procedures and avoid duplicate blood draws on the same day—following Screening procedures, only the following Dosing Visit 1 procedures will be performed:

- Concomitant medications
- Vital signs relative to study drug administration
- Study drug administration
- Daily angioedema attack monitoring and study diary
- Adverse event monitoring
- PK/PD and immunogenicity (C1 INH antibody) blood sampling
- Quality of life questionnaire

6.1 Medical History and Physical Examination

A medical history will be taken at the screening visit. All medical history findings that have been present/active within the 5 years before enrollment will be recorded in the CRF regardless of clinical relevance or presence at study start. Medical history findings that have not been present within the 5 years before enrollment will be recorded if deemed clinically relevant to the conduct of the study by the Investigator. The medical history should include any history of allergic reactions to drugs. In addition, the following information associated with the history of angioedema will be recorded in the CRF:

- HAE Type (I or II). If a subject does not have a confirmed diagnosis of HAE based on historical data, including C1 INH functional deficiency, the subject's diagnosis must be confirmed prior to treatment by C1 INH test results which demonstrate a quantitative and/or functional C1 INH deficiency; a blood sample may be collected at screening to determine a deficiency in the levels of C1 INH and/or C1 INH activity.
- Family history of HAE within first degree relatives (offspring, siblings, parents).
- If a central line has ever been used for administration of any medication, and if yes, is there currently a central line in place?
- Estimated onset date of last angioedema attack before enrollment (ie, prior to Day 1).

- Total number, typical locations, average overall duration (in days), and average overall severity of angioedema attacks experienced during the 3 consecutive months before the first dose.
- Visual Analogue Scale (VAS) typical score for the subject's angioedema attack pain during the 3 consecutive months before the first dose. Note: Subjects younger than 5 years of age do not need to complete the VAS.

The Investigator or designee will perform physical examinations at the time points specified in Schedule 1 and Schedule 3. Physical examinations will be performed in accordance with standard practices at the study site. Physical examination abnormalities observed at the screening visit will be recorded as medical history. New abnormalities or worsened pre-existing abnormalities observed post-screening should be recorded as AEs, as determined by the Investigator (see Section 9).

Body weight and height will be measured at the time points specified in Schedule 1 and Schedule 3.

6.2 Adverse Event Collection

At each study visit, subjects will be questioned in a general way to ascertain if AEs have occurred since the previous visit (eg, "Have you had any health problems since your last visit?"). Adverse events will be collected from the time informed consent is signed through 7 days after the last dose of investigational product. This includes events occurring during the screening phase of the study, regardless of whether or not the investigational product is administered. In addition, the investigator will report all SAEs that occur through 30 days after the last dose of investigational product to PAREXEL International Pharmacovigilance and the respective Independent Reviewing Authority according to local reporting requirements.

Please refer to Section 9, Adverse and Serious Adverse Events Assessment.

6.3 Vital Signs

Blood pressure (BP) and pulse will be measured at the time points specified in Schedule 1 and Schedule 3. Additional vital signs measurements may be performed during the study if clinically indicated. On dosing days, vital signs should be obtained ≤30 minutes before the start of the infusion, ≤15 minutes after completion of the infusion, and between 30 minutes and 1 hour after completion of the infusion. Vital sign measurements will not be collected at Visits 10, 12, 14, 18, 20, and 22 from subjects who independently self-administer investigational product at home. At applicable visits, every effort should be made to measure vital signs before the collection of blood samples.

6.4 12-Lead Electrocardiogram

Subjects will have a 12-lead ECG recorded as specified in Schedule 1. Additional ECGs may be performed during the study if clinically indicated. The following ECG data will be recorded in the CRF: HR, PR interval, QRS duration, QT interval, and QTc interval. The Investigator will

be responsible for providing the interpretation of all ECGs (clinically significant/not clinically significant).

6.5 Prior and Concomitant Medications

Prior and concomitant medications to be recorded at each visit include prescription medications, blood products (eg, albumin, packed red blood cells, whole blood, fresh frozen plasma, platelets), dietary supplements/vitamins, electrolyte supplementation, and over-the-counter medications. Topical medications will be recorded only if used to treat an AE.

6.5.1 Prior Medications

A medication history will be taken at the screening visit and updated before the first dose on Day 1 to ensure that the subject remains eligible for study participation. Any therapy received for the management of HAE within 12 months before Day 1 should be recorded, including overall start and stop dates (if known) and the HAE indication (ie, long-term prevention, acute treatment, short-term prevention). All other medications taken within 1 week before Day 1 will be recorded in the CRF. In addition, any medications taken for an AE prior to Day 1 will be recorded.

